#### 14.4.1 Definitions

The definitions for protocol violation and deviation as described by the MD Anderson IRB will be applied for reporting purposes for all institutions participating in the trial.

Protocol Deviation: Noncompliance with the protocol that does not have a significant effect on the subject's rights, safety, welfare, and/or the integrity of the data. Deviations may be caused by the action of the subject, the investigator, the research staff, or natural events.

Protocol Violation: Changes to protocol procedures without prior approval of the IRB/Sponsor. Violations may significantly alter the clinical effectiveness of the treatment or the evaluation of its toxicity and adversely affect patient's safety and rights.

Unanticipated Problems: An incident, experience or outcome, that is unexpected, related or possibly related to participation in the research and suggests that the research places subjects or

others at a greater risk of harm (including physical, psychological, economic, or social harm) that was previously known or recognized. These incidents do not meet the definition of an adverse event. Unanticipated problems are not limited to study participants, and may also include others such as family members and research staff.

MD Anderson GU Department: Upon receipt of the violation/deviation/unanticipated problem report from the participating institution, the Protocol Chair will review and submit the report to the MD Anderson IRB for review.

#### 14.5 Research Team Teleconferences

The MD Anderson and participating institution's PIs and study teams will participate in teleconferences as needed to discuss the following information:

- Status of patients enrolled at sites including
- Eligibility for trial
- Status of treatment
- Adverse Events
- Response evaluation
- Any questions or concerns

#### 15.0 DATA AND PROTOCOL MANAGEMENT

Protocol Compliance: All required interim and pretreatment data should be available, and the physician must assess tumor response and must provide a detailed description of toxicity, when appropriate. If dose modifications or treatment interruptions are necessary, the details must be carefully documented. Performance status must be documented at each toxicity assessment.

Data Capture: Data will be entered in the MD Anderson GU departmental oracle system. Registration data entry and randomization will occur prior to initiation of therapy. All eligibility criteria must be satisfied.

Accuracy of Data Collection: The MD Anderson Principal Investigator will be the final arbiter of response and toxicity, should a difference of opinion exist.

#### 15.1 Schedule of Data Submission

MD Anderson protocol specific Case Report Forms and/or electronic Case Report Forms will be used for collection of all study data. The schedule for submission of case report forms is as follows:

Case Report Forms/Source Documents	Schedule for Submission
Informed Consent/Patient Authorization for the Release of Personal Health Information	Prior to study registration
Eligibility Checklist	Prior to study registration
On-Study Form Supporting Source Documents (e.g. Pathology reports, Medical Administration Records, Radiology/Laboratory Reports, History and Physical, Progress Notes)	14 days after treatment initiation
Chemotherapy/Treatment by Cycle Form (Chemotherapy, Laboratory Results, Concomitant Medications) Supporting Source Documents	14 days after cycle completion
Adverse Event Form Supporting Source Documents	14 days after cycle completion
Response Assessment Forms (Disease Measurements) Supporting Source Documents	14 days after protocol defined imaging assessment
Off Treatment Supporting Source Documents	14 days after last treatment date
Survival Update Form Supporting Source Documents	14 days after protocol defined survival review
Off Study Form Supporting Source Documents	14 days after patient removed from study

# 16.0 STATISTICAL CONSIDERATIONS

# 16.1 Definition of primary outcome/endpoint:

Composite rate of toxicity defined as the percentage of patients who experience one or more of the following  $\geq$ grade 3 toxicities using CTCAE version 4.03 criteria that are possibly, probably, or definitely related to study therapy: fatigue, HFS or diarrhea.

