Table 1: Comparison of the incidence of selective toxicities of VEGFR inhibitors in metastatic renal cell carcinoma

		Fat	igue	Н	FS	Dia	rrhea	Low 1	Platelets
	No. of patient	All grade	Grade 3+	All grade	Grade 3+	All grade	Grade 3+	All grade	Grade 3+
	S			Suniti	nib				
Phase III vs. IFN 	375	54%	11%	29%	9%	61%	9%	68%	9%
EFFECT 	146	65%	9%	32%	10%	59%	6%	75%	13%
COMPARZ 	548	63%	7%	50%	12%	57%	8%	34%	16%
CCF 2/1 	30	54%	7%	17%	0%	36%	3%	7%	0%
MDACC*	-	62%	-	32%	-	32%	-	3%	-

before modification									
MDACC*	-	19%	-	2%	-	2%	-	0%	-
after									
modification									
				Pazopa	anib				
Phase III 	290	19%	2%	<10%	<1%	52%	4%	32%	1%
	554	55%	11%	29%	6%	63%	9%	10%	3%
COMPARZ 									
				Tivoza	nib				
Phase III 	259	19%	3%	13%	2%	18%	2%	17%	1%

\*unpublished data

Table 2: Prevalence of toxicity before and after schedule modification

(MD Anderson Cancer Center data)

Adverse Event	Before schedule modification N = (%)	At first follow up after schedule modification $N = (\%)$
Fatigue	40 (64)	18 (29)
Hand foot syndrome	24 (38)	6 (10)
Diarrhea	20 (32)	4 (6)
Mucositis	14 (22)	3 (5)
Nausea/vomiting	9 (14)	7 (11)
Dysgeusia	6 (10)	0
Rash	6 (10)	0
Hypertension	6 (10)	3 (5)
Anorexia	5 (8)	1 (1.5)
Mouth sores	3 (5)	0
Laboratory Abnormalities	1	
ANC < 1K/uL	3 (5)	1 (1.5)
Platelet count < 100 K/uL	2 (3)	1 (1.5)
TSH level > 4.20 IU/mL	2 (3)	0

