# 2.0 OBJECTIVES

# 2.1 Primary Objective

To assess the incidence of  $\geq$  grade 3 treatment-related fatigue, hand-foot syndrome and/or diarrhea in metastatic renal cell carcinoma (mRCC) patients receiving sunitinib on a 2 weeks on / 1 week off schedule (schedule 2/1).

[figure not shown]

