#### 8.2.4 Attribution

Attribution is the relationship between an adverse event or serious adverse event and the study drug. Attribution will be assigned as follows:

- Definite The AE is clearly related to the study drug.
- Probable The AE is likely related to the study drug.
- Possible The AE may be related to the study drug.
- Unlikely The AE is doubtfully related to the study drug.
- Unrelated The AE is clearly NOT related to the study drug.

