## 16.3 Sample size justification:

The primary goal of the trial is to estimate the likelihood that with a 2 weeks on/1 week off schedule a patient will experience at least one of the most commonly reported and troublesome grade 3 or worse sunitinib-related toxicities – fatigue, hand-foot syndrome, and diarrhea. The primary endpoint is the percentage of patients who experience one or more of these adverse events. A total of 60 patients will be accrued in order to estimate the likelihood of toxicity using a 95% confidence interval that has a half-width of <10% (assuming the observed composite toxicity rate is approximately 10-15%). If the upper bound of the confidence interval is less than 25% this will be taken as an indication that the 2/1 schedule has a better toxicity profile than the standard 4/2 schedule since from earlier randomized studies approximately 25-30% of patients on the 4/2 schedule can be expected to have these toxicities

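### The primary composite counts only drug-attributed events, but the attribution basis of the 4/2 rates behind its 25% bound is not given, and no all-cause check is planned

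*Combined protocol and SAP*

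**What the plan says.** Section 16.1 defines the endpoint as the percentage of patients with at least one grade 3 or worse event, limited to those "that are possibly, probably, or definitely related to study therapy: fatigue, HFS or diarrhea". Section 2.1 agrees, asking about "treatment-related fatigue, hand-foot syndrome and/or diarrhea in metastatic renal cell carcinoma (mRCC) patients receiving sunitinib". Of the five attribution categories in section 8.2.4, the lowest two do not count. One of these reads "Unlikely The AE is doubtfully related to the study drug"; the other is clearly unrelated.

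Section 16.3 states that "A total of 60 patients will be accrued in order to estimate the likelihood of toxicity using a 95% confidence interval" and then sets the decision rule. An upper limit below 25% indicates a better toxicity profile than 4/2, "since from earlier randomized studies approximately 25-30% of patients on the 4/2 schedule can be expected to have these toxicities". Earlier in that paragraph the toxicities are called sunitinib-related.

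The 4/2 data are in section 1.4, under "Table 1: Comparison of the incidence of selective toxicities of VEGFR inhibitors in metastatic renal cell carcinoma". The table does not say whether its rates are treatment-related or all-cause.

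The study is single-arm (section 3.1), and no independent review of attribution is described. Section 15.0 says: "The MD Anderson Principal Investigator will be the final arbiter of response and toxicity, should a difference of opinion exist". The secondary endpoint on all grade 3 or worse toxicities (section 16.2) has the same relatedness filter. Section 16.4 tabulates toxicities by type and grade, but plans no patient-level composite regardless of attribution.

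**The concern.** The rule compares a rate filtered by unblinded judgement with an external figure whose filter is unknown. If the cited 4/2 trials counted events whatever their cause, each patient whose only qualifying event is rated unlikely or unrelated lowers the 2/1 rate and leaves the benchmark where it was. Such an error can only favour 2/1. The rule is the trial's only formal basis for saying that 2/1 is better tolerated than 4/2, and no planned analysis would show whether that conclusion depends on attribution.

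**Working it through.** **Inputs.** N = 60, the 25% bound and the 25-30% benchmark are from section 16.3. Grade 3 or worse rates on 4/2 (fatigue, HFS, diarrhea) are from Table 1:

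- phase III against interferon: 11%, 9%, 9%
- randomized phase II of intermittent against continuous dosing: 9%, 10%, 6%
- phase III against pazopanib: 7%, 12%, 8%

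**The plan's precision figure.** Section 16.3 aims for a half-width below 10 points, "assuming the observed composite toxicity rate is approximately 10-15" percent. The Wald half-width is 1.96 × √(p(1−p)/60), which is 7.6 points at 10% and 9.0 at 15%. The exact (Clopper-Pearson) half-widths are 8.4 and 9.7. The stated precision is reproduced.

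**Likely source of the benchmark.** The simple sums are 11 + 9 + 9 = 29%, 9 + 10 + 6 = 25% and 7 + 12 + 8 = 27%. They fall in the 25-30% range, so Table 1 is the probable source. This is an inference; section 16.3 does not name its source.

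**The rule as a count.** Section 16.4 does not name an interval method, so both common ones are shown.

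- Wald: the upper limit is 24.0% at 9/60 and 26.1% at 10/60, so the rule passes at 9 or fewer.
- Exact: the upper limit is 24.6% at 8/60 and 26.6% at 9/60, so the rule passes at 8 or fewer. Wilson gives the same cutoff (24.2% and 26.1%).

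**Effect of excluding events.** Let q be the true all-cause rate on 2/1 and m the share of patients with events who are not counted. The counted number is X ~ Binomial(60, q(1−m)), and the chance of passing is P(X ≤ 8) for exact or P(X ≤ 9) for Wald. The documents give no value for m, so a range is shown. Both values of q mean no advantage over 4/2 if the benchmark is all-cause.

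| m | q = 25%, exact | q = 25%, Wald | q = 30%, exact | q = 30%, Wald |
|---|---|---|---|---|
| 0% | 2.1% | 4.5% | 0.2% | 0.6% |
| 10% | 5.5% | 10.5% | 0.9% | 2.1% |
| 20% | 12.7% | 21.3% | 3.2% | 6.4% |
| 30% | 25.5% | 38.0% | 9.2% | 16.3% |

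**How much exclusion is plausible?** At q = 25% the expected count is 0.25 × 60 = 15. To pass at that count, 15 − 9 = 6 (Wald) or 15 − 8 = 7 (exact) of the 15 would have to be excluded, which is 40% or 47%. If only fatigue were attributed to the disease, with no overlap between components, losing 20% of events means losing this share of grade 3 or worse fatigue:

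- 0.20 × 29 / 11 = 53%
- 0.20 × 25 / 9 = 56%
- 0.20 × 27 / 7 = 77%

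Losing half of the fatigue events gives composites of 23.5%, 20.5% and 23.5%, with pass chances of about 4-11% (exact) or 8-19% (Wald).

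**If the benchmark is treatment-related.** Both sides then carry the same filter. At a true related rate of 25% the pass chance stays at 2.1% or 4.5%.

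**The case against.** The strongest reply is that section 16.3 does give a basis: the phrase about 4/2 patients refers back to toxicities described as sunitinib-related, in line with sections 2.1 and 16.1. This stands for the wording of the rule. It does not show how the cited trials counted events. Where section 1.3.6 reports treatment-related rates it says so; Table 1 does not.

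A reader might infer from the word incidence in Table 1 that the benchmark is all-cause. The documents do not support that. Sections 2.1 and 16.2 use the same word for rates limited to related events, and the table's title speaks of toxicities of the drugs.

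A reader might also infer that disease fatigue, attributed away, could by itself produce the claimed advantage. That goes too far:

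- Possibly related events still count, so only the two lowest categories are lost.
- Sections 1.3.6 and 8.1.1 describe fatigue as the primary dose-limiting toxicity of sunitinib, and section 4.1 admits only ECOG 0-1.
- At grade 3 or worse, fatigue is the commonest component in one of the three 4/2 trials (11% against 9%). HFS leads in the other two (10% against 9%, 12% against 7%).
- The principal investigator decides toxicity only where opinions differ.

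Nor should a pass at a true all-cause rate of 20% be called a false positive: 20% is a real advantage over 25-30%.

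Finally, a compulsory all-cause criterion would have a price. If the benchmark is treatment-related, with a related rate of 10% and an all-cause rate of 12.5%, requiring the all-cause composite to pass lowers the exact-rule chance from 86% to 67%. That argues against a hard second gate. It does not argue against reporting the all-cause result.

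**Conclusion.** The point holds as a conditional one. The endpoint is filtered by unblinded attribution, the basis of the 4/2 source rates is not given, and nothing planned would reveal dependence on the filter. If those rates are all-cause and the true all-cause rate on 2/1 is 25%, excluding 10-20% of patients with events raises the false-pass chance from 2.1% to 5.5-12.7% (exact) or from 4.5% to 10.5-21.3% (Wald). The risk is smaller at a true 30%. The excluded shares are assumptions. If the source rates are treatment-related, there is no definitional mismatch. The documents do not settle which case applies, so they do not support a statement that the comparison is biased, only that its comparability is asserted and not shown.

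**What to change.** - **Section 16.4:** prespecify a sensitivity analysis of the same patient-level composite, counting grade 3 or worse fatigue, HFS or diarrhea regardless of attribution. Report its 95% interval, by the same method as the primary one, beside the primary result and against the 25% bound.
- **Section 16.3:** state the source and attribution basis of the 25-30% figure. If the basis is all-cause or cannot be established, say that the conclusion over 4/2 will be qualified when the all-cause upper limit is not below 25%.
- If the benchmark is shown to be treatment-related, keep the all-cause result as supporting information and do not make it a mandatory second criterion.

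The cost is a few sentences, a check of the cited 4/2 sources, and one more line in the results. Section 8.3 already requires grade and attribution for every adverse event, so no new data are needed. The downside is that the all-cause rate will be equal to or less favourable than the primary one.

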# 16.2 Definition of secondary outcomes/endpoints:

- Progression-free survival (PFS) defined as the time from treatment initiation to disease progression using RECIST v 1 or death.
- Incidence of all ≥grade 3 toxicities per CTCAE version 4.03 criteria, defined as the percentage of patients who experience any grade 3 or greater toxicity that is possibly, probably, or definitely related to study therapy.
- Dose reductions, dose interruptions, dose delays will be recorded using pill diaries
  maintained by patients that will be reviewed and recorded at each visit. This outcome will be
  reported as the percentage of patients who underwent one or more dose reductions, dose
  interruptions and/or treatment delays. The number of patients who discontinue treatment due
  to unacceptable toxicities will be recorded, and reported as a percentage of the total number
  of enrolled patients.
- Changes in the patient reported outcomes in FACT-G (general) scale during treatment on schedule 2/1
- Changes in circulating DNA levels with antiangiogenic treatment
- Correlation of tumor associated macrophages (TAM) with response to therapy

## 16.3 Sample size justification:

The primary goal of the trial is to estimate the likelihood that with a 2 weeks on/1 week off schedule a patient will experience at least one of the most commonly reported and troublesome grade 3 or worse sunitinib-related toxicities – fatigue, hand-foot syndrome, and diarrhea. The primary endpoint is the percentage of patients who experience one or more of these adverse events. A total of 60 patients will be accrued in order to estimate the likelihood of toxicity using a 95% confidence interval that has a half-width of <10% (assuming the observed composite toxicity rate is approximately 10-15%). If the upper bound of the confidence interval is less than 25% this will be taken as an indication that the 2/1 schedule has a better toxicity profile than the standard 4/2 schedule since from earlier randomized studies approximately 25-30% of patients on the 4/2 schedule can be expected to have these toxicities

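### Section 16.3 draws a conclusion about the whole toxicity profile of 2/1 from an endpoint and benchmark that cover only grade 3+ fatigue, hand-foot syndrome and diarrhea

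*Combined protocol and SAP*

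**What the plan says.** Objective 2.1 concerns grade 3 or worse "treatment-related fatigue, hand-foot syndrome and/or diarrhea in metastatic renal cell carcinoma (mRCC) patients" on the 2/1 schedule. Section 16.1 defines the endpoint as the percentage of patients with one or more grade 3 or worse events "that are possibly, probably, or definitely related to study therapy: fatigue, HFS or diarrhea".

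Section 16.3 describes the aim as estimating the chance that a patient has "at least one of the most commonly reported and troublesome grade 3 or worse sunitinib-related toxicities", and then names the same three. It plans 60 patients for a 95% confidence interval with a half-width under 10 percentage points at an observed rate of about 10-15%. If the upper bound is below 25%, "this will be taken as an indication that the 2/1 schedule has a better toxicity profile than the standard 4/2 schedule". The reason given is that about 25-30% of patients on 4/2 can be expected to have the named toxicities.

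All related grade 3 or worse toxicity is a secondary endpoint (16.2), reported with a 95% confidence interval (16.5). It has no 4/2 benchmark and no part in the rule.

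**The concern.** The rule's input is three symptoms; its output is a statement about the toxicity profile. Nothing in 16.3 limits that term to the three. As written, the rule would support the statement even if other grade 3+ toxicity, or grade 3+ toxicity as a whole, were unchanged or worse on 2/1.

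This matters because the trial has one arm and is read against historical figures. The pre-specified sentence in 16.3 is what a report would cite as its comparative conclusion. The protocol's own background also shows that grade 3+ toxicity outside the composite is not rare on sunitinib:

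- Table 1 lists low platelets next to the three components.
- Section 1.3.6 names fatigue (8.2%), hypertension (5.8%) and neutropenia (5.8%) as the most common related grade 3 events in solid-tumor patients. Two of those three lie outside the composite.
- Section 8.1.1 counts neutropenia and thrombocytopenia among the most frequent events of greatest severity.

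**Working it through.** **1. The plan's own figure.** Inputs from 16.3: n = 60, observed rate p of 10-15%, 95% interval. Wald half-width = 1.96 × √(p(1−p)/n).

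- p = 0.10: 1.96 × √(0.09/60) = 7.6 points.
- p = 0.15: 1.96 × √(0.1275/60) = 9.0 points.

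The exact (Clopper-Pearson) half-widths are 8.4 and 9.7 points. All are below 10, so the precision statement reproduces.

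**2. What the rule responds to.** At n = 60 the upper bound is below 25% with at most 9 composite events (Wald) or at most 8 (Wilson or Clopper-Pearson). If the true composite rate were 25%, the chance of meeting the rule would be 4.5% or 2.1% respectively. The rule therefore controls error for the composite. It uses nothing else: with 8 composite events (exact upper bound 24.6%) it is met whatever other grade 3+ toxicity any of the 60 patients has.

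**3. What the benchmark covers.** Grade 3+ rates on 4/2 from Table 1, section 1.4:

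| Trial | n | Fatigue | HFS | Diarrhea | Low platelets |
|---|---|---|---|---|---|
| Phase III vs IFN | 375 | 11% | 9% | 9% | 9% |
| EFFECT | 146 | 9% | 10% | 6% | 13% |
| COMPARZ | 548 | 7% | 12% | 8% | 16% |

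The sums of the three components are 11+9+9 = 29%, 9+10+6 = 25% and 7+12+8 = 27%, which fall in the stated 25-30%. With low platelets added they become 38%, 38% and 43%. These sums assume that no patient has two of the events, so they are ceilings; the overlap is not given. Assuming independence instead gives 26.3%, 23.0% and 24.7% for three items, and 32.9%, 33.0% and 36.8% for four. Either way, the 25% threshold belongs to the three-item composite.

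**4. Where the omitted toxicity stands.** Weighted by patient number, N = 375+146+548 = 1069:

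- Low platelets: (9×375 + 13×146 + 16×548)/1069 = 13.1%
- HFS: (9×375 + 10×146 + 12×548)/1069 = 10.7%
- Fatigue: (11×375 + 9×146 + 7×548)/1069 = 8.7%
- Diarrhea: (9×375 + 6×146 + 8×548)/1069 = 8.1%

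Low platelets is the highest of the four when pooled, in EFFECT (13% against at most 10%) and in COMPARZ (16% against at most 12%). In the phase III trial against IFN, fatigue is highest (11% against 9%).

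For scale only, 9-16% of 60 is 5.4 to 9.6 patients. This applies 4/2 rates to a trial without 4/2 patients and is not a forecast for 2/1.

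**The case against.** The best defence is that the text largely limits itself. The sentence speaks of an indication, gives the rate of the named toxicities as its ground, and follows an objective, a hypothesis (1.4) and an endpoint definition that all name the three events. Sections 16.4 and 16.5 also tabulate all toxicities by type and grade, and the any-grade-3+ rate gets an interval. This stands as a limit on the harm: a careful reader will know what was measured. It does not make the concluding phrase match the endpoint.

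Four stronger readings are tempting, and the documents do not support them.

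- *Low platelets is the most frequent grade 3+ toxicity of 4/2.* Table 1 is headed "Comparison of the incidence of selective toxicities of VEGFR inhibitors in metastatic renal cell carcinoma" and has four entries, so it cannot rank all toxicities. In one of its three trials fatigue is higher. Section 1.3.6 does not list thrombocytopenia among the most common related grade 3 events.
- *Table 1 contradicts the reason given for choosing the three.* The criterion is joint: commonly reported and troublesome. Section 1.2 reports fatigue and diarrhea as the most troublesome to patients. Section 1.4 reports fatigue, HFS and diarrhea as prompting schedule change in 64%, 38% and 32%. The choice of endpoint can stand.
- *The omission favours 2/1.* Nothing points that way. Table 1 shows 0% grade 3+ low platelets in the 30-patient 2/1 series, and Table 2 shows platelet counts below 100 K/uL falling from 3% to 1.5% after schedule modification. The evidence is thin, since 0 of 30 has an exact 95% upper limit of 11.6%, but it gives no support to the suspicion.
- *A wider claim could be allowed if the platelet and any-grade-3+ rates compare well with 4/2.* The documents give no any-grade-3+ rate for 4/2. A platelet comparison with 9-16% would be unsafe. Scheduled on-treatment blood counts fall on Day 42 (3.2, 12.2), at the end of an off week (6.1), and a laboratory abnormality is reported as an adverse event only under the conditions in 8.3. The documents do not say how the Table 1 platelet rates were ascertained.

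**Conclusion.** The point holds as one of wording and scope. The conclusion in 16.3 is wider than the endpoint in 16.1, objective 2.1 and its own benchmark, and the rule cannot register any other grade 3+ toxicity. That includes low platelets, at 9-16% on 4/2 by trial and 13.1% pooled.

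The endpoint, the 60 patients, the 25% threshold and the analysis are unaffected. What changes is the claim the trial may make if the rule is met. A reader might go further and infer that the composite was chosen to flatter 2/1 or that its justification is false; the documents support neither.

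This rests on reading toxicity profile in its ordinary sense, and on pooling the rounded percentages of Table 1 by patient number.

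**What to change.** In 16.3, replace the statement that 2/1 has a better toxicity profile than 4/2 with the statement that it has a lower incidence of related grade 3 or worse fatigue, hand-foot syndrome or diarrhea than 4/2. Report the any-grade-3+ rate already planned in 16.5, with its 95% confidence interval, beside the primary result as descriptive context. State that no wider claim about the toxicity profile will be made from this rule.

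Keep the endpoint, its rationale and the threshold as they are. Adding low platelets to the composite would require a new threshold, because 25% was set for three components. Do not add a platelet benchmark as a condition.

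The cost is a few words in 16.3 and the placement of one result that is already planned. The downside is a narrower headline claim.
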